4. STUDY DESIGN

4.1 General Study Design and Plan

This is a multicenter randomized, double-blind, placebo-controlled Phase 2 study to evaluate oral ifetroban administered daily for eight weeks in symptomatic AERD subjects. The clinical study will be conducted with 3 periods:

- Screening period of up to two weeks
- Randomized ifetroban/placebo treatment period of eight weeks
- Post-treatment period for safety and efficacy of two weeks

Study Design

PBO= placebo; PD= pharmacodynamic; SNOT= Sino-nasal Outcome Test; ACQ= Asthma Control Questionnaire; TNSS= Total Nasal Symptom Score; FEV1= forced expiratory volume in one second; PNIFR= peak Nasal Inspiratory Flow Rate; FeNO= Fractional exhaled nitric oxide; UPSIT= Smell Identification Test

4.2 Study Population

Approximately 76 subjects are to be randomized into two treatment groups with 38 subjects per group.

Individuals who meet all of the following criteria are eligible for enrollment as study subjects:

1. History of physician-diagnosed asthma
2. History of nasal polyposis
3. History of at least two reactions to oral aspirin or other nonselective cyclooxygenase inhibitor with features of lower airway involvement (cough, chest tightness, wheezing, dyspnea), or diagnosis of AERD via a physician-conducted challenge to aspirin in the last five years before starting treatment
4. Stable asthma (post-bronchodilator FEV1 of $\geq 60\%$, no glucocorticoid burst for at least two weeks prior to starting treatment, no hospitalizations or emergency room visits for asthma at least three months prior to starting treatment and not on a dose $>1000\text{ }\mu\text{g}$ fluticasone or equivalent daily).
5. ≥ 18 years of age
6. Exhibit symptomatic AERD within two weeks of starting treatment by demonstrating a score of at least 20 on the SNOT – 22

Individuals who meet any of these criteria are not eligible for enrollment as study subjects:

1. Current smoking, defined as daily tobacco smoking in the last six months and at least one instance of tobacco smoking in the last three months
2. Current pregnancy or breastfeeding
3. Use of oral or systemic steroids (e.g. prednisone or equivalent) $> 20\text{ mg}$ daily in the last four weeks before starting treatment
4. Daily use of long-acting antihistamines, 5-lipoxygenase inhibitors (e.g. zileuton) and leukotriene receptor antagonists (e.g. montelukast) in the last two weeks before starting treatment
5. Less than 12 months of allergy shots (maintenance dose of allergy shots are allowed if treatment duration exceeds 12 months)
6. Any use of nonsteroidal anti-inflammatory drugs (NSAIDs) or any drug that inhibits the cyclooxygenase enzyme in the last two weeks before starting treatment
7. History of bleeding diathesis or use of anticoagulant or antiplatelet drugs in the last 2 weeks before starting treatment
8. Any immunosuppressive treatment including but not limited to methotrexate, cyclosporine, mycophenolate, tacrolimus, gold, penicillamine, sulfasalazine, hydroxychloroquine, azathioprine, cyclophosphamide, and immunotherapy in the last two weeks before starting treatment (maintenance dose of allergy shots are allowed if treatment duration exceeds 12 months)
9. Endoscopic sinus surgery / polypectomy within the past three months
10. Previously treated in any clinical trial with ifetroban
11. Previously treated with other investigational drugs within eight weeks or five half-lives, whichever is longer, before screening

12. Conditions/concomitant disease which make the participant unevaluable for the efficacy endpoints

4.3 Randomization and Blinding

Subjects who meet all the inclusion and no exclusion criteria during the Screening/Baseline Period will be randomized using a 1:1 randomization ratio to receive either ifetroban 200 mg once daily or matching placebo. A central randomization will be utilized. Approximately 76 subjects shall be randomized to ensure at least 38 subjects per group will be analyzed for efficacy

The study will be double blind with respect to the treatment assignment. To maintain the study blind, the appearance of packaging and capsules will be identical in both study arms. Site and CPI clinical staff will be blinded to the treatment assignment until the completion of the study. Individual treatment assignment will remain blinded throughout the study. In the event a treatment assignment needs to be unblinded for safety reasons, the site principal investigator will notify the study project manager, who will consult with the medical monitor. The medical monitor will review the circumstances and grant approval as indicated. Any intentional or unintentional breaking of the blind will be reported to the Sponsor immediately and fully documented in the subject's case report form.

4.4 Study Assessments

Schedule of Treatment & Events

	Screening Period	Treatment Period				Post-treatment Period
	Visit(s)	Visit	Phone Call	Visit	Visit	Visit
	Week -2 to Week 0	Week 0	Week 1	Week 4 (± 2 days)	Week 8 (± 2 days)	Week 10 (± 2 days)
Informed Consent	X					
Inclusion/Exclusion Criteria	X					
Medical & Surgical History	X					
Subject Demography	X					
Physical Exam with vital signs	X					
Limited Physical Exam with vital signs		X		X	X	X
Spirometry (FEV1)	X	X		X	X	X
PNIFR and FeNO		X		X	X	X
Pregnancy Test (Serum/Urine)^a	X	X		X	X	X
Hematology^b	X	X ^d			X	X ^e
PT, INR, Chemistry^c	X	X ^d			X	X ^e
SNOT-22, TNSS, ACQ-7	X ^f	X		X	X	X
Smell test (UPSIT)		X		X	X	X
Collect urine & blood for eicosanoid levels		X		X	X	X
Collect nasoabsorptive matrix for eicosanoid levels		X		X	X	X
Self-assessment of the treatment (optional)					X	
Dispense IMP		X		X		
IMP Dosing		I-----Continual Once Daily Dosing (200 mg/day)-----I				
Record Concomitant Medications	I-----	Continual-----				I-----
AE/SAE Recording (if any)		I-----	Continual-----			
Dispense, review and/or collect subject diary		X		X	X	X

a. For women of childbearing potential;

b. Hemoglobin, hematocrit, platelet count, total white blood cell count with five-part differential count, and total red blood cell count.

c. Creatinine, blood urea nitrogen, glucose, uric acid, total cholesterol, total protein, albumin, total bilirubin, alanine aminotransferase, aspartate aminotransferase, alkaline phosphatase, electrolytes (sodium, potassium, chloride), bicarbonate, and creatine phosphokinase

d. Week 0 hematology, chemistry, PT and INR do not have to be repeated if Screening labs were performed within 2 weeks of starting IMP

e. Week 10 hematology, chemistry, PT and INR only performed for abnormal labs at Week 8

f. SNOT-22 only at Screening; All 3 questionnaires are required at subsequent visits.

FEV1= Forced Expiratory Volume in 1 Second; PNIFR= Peak Nasal Inspiratory Flow Rate; FeNO= Fractional exhaled Nitric oxide; PT= prothrombin time; INR= international normalized ratio; SNOT= Sino-nasal Outcome Test; TNSS= Total Nasal Symptom Score; ACQ-7= Asthma Control Questionnaire; UPSIT= Smell Identification Test; IMP= Investigational Medicinal Product; AE= adverse event; SAE= serious adverse event

4.5 Sample Size Determination

Thirty-eight subjects per group will provide 90% power for the comparison of ifetroban and placebo with respect to the change from baseline in SNOT-22 scores at Week 8 (two-sided, level 0.05), assuming a common standard deviation of 16 and a true difference is 12.

4.6 Study Variables

Efficacy Variables

- SNOT-22 score (Sino-Nasal Outcome Test)
 - Total Score = Sum of the values collected in the 22 questions collected in the database.
 - CFB (change from baseline) total score = post-treatment measurement - baseline
 - PCFB (percent change from baseline) = (post-treatment measurement – baseline)/baseline
 - Improvement in SNOT-22 (Yes or No): if CFB (SNOT-22) <0, then improvement = 'Yes'; otherwise improvement = 'No'
 - Nasal Related Subscale = sum of the following questions to calculate the subscale: "need to blow nose", "sneezing", "runny nose", "nasal obstruction", "loss of smell/taste", and "post-nasal drip",
 - Ear and Facial Related Subscale = sum of the following questions to calculate the subscale: "ear fullness", "dizziness", "ear pain", "facial pain and pressure"
 - Quality of Life Related Subscale = sum of the following questions to calculate the subscale: "difficulty falling asleep", "wake up at night", "wake up tired", "fatigue", "reduced productivity", "reduced concentration"
 - Psychologically Related Subscale = sum of the following questions to calculate the subscale: "frustrated/restless/irritable", "sad", "embarrassed"
 - CFB Nasal Related Subscale = post-treatment measurement visit - baseline
 - CFB Ear and Facial Related Subscale = post-treatment measurement visit – baseline
 - CFB Quality of Life Related Subscale = post-treatment measurement visit - baseline
 - CFB Psychologically Related Subscale = post-treatment measurement visit - baseline
- Forced Expiratory Volume 1 (FEV1)
 - FEV1 Value = Collected on the CRF. Measured as the "best effort" of the 3 collected measurements at each time point where "best effort"= Max (fev1_1, fev1_2, fev1_3)
 - CFB FEV1 = post-treatment measurement – baseline

- Peak Nasal Inspiratory Flow Rate (PNIFR)
 - PNIFR value= Measured as the “best effort” of the 3 collected measurements at each time point where “best effort”= Max(pnfr1, pnfr2, pnfr3)
 - CFB PNIFR = post-treatment measurement - baseline
- University of Pennsylvania Smell Identification Test (UPSIT)
 - UPSIT value - Calculated by staff. Found in the database.
 - CFB UPSIT= post-treatment measurement – baseline
- Fractional exhaled Nitric Oxide (FeNO)
 - FeNO value – Collected on the CRF.
 - CFB FeNO = post-treatment measurement - baseline
- Asthma Control Questionnaire (ACQ) – average of non-missing values
 - ACQ score. Calculated in database (ACQ_Score)
 - CFB ACQ = post-treatment measurement – baseline
 - Any improvement in ACQ-7 (Yes or No): If CFB ACQ<0, then improvement =’Yes’; otherwise improvement = ‘No’
- Total Nasal Symptom Score (TNSS) AM and PM measurements
 - TNSS Daily Score = sum of the 4 symptom scores (congestion, runny_nose, nasal_itching, sneezing) for both AM and PM, separately. (listed only)
 - TNSS Visit Score: The daily score for AM and PM are averaged over time between the visits separately. Baseline Visit Score for AM and PM is obtained by averaging over the screening period and the day of the baseline visit. Week 4 Visit Score is obtained by averaging over the day after the baseline visit to the day of the Week 4 visit. Week 8 Visit Score is obtained by averaging over the day after Week 4 visit to the day of the Week 8 visit. Week 10 Visit Score is obtained by averaging over the day after Week 8 visit to the day of Week 10 visit.
 - CFB TNSS Visit Score = post-treatment measurement – baseline
- Frequency and Severity of Asthma Exacerbations (Respiratory Reaction Questionnaire)
 - Subject Frequency =count the number of reports since the previous visit for each visit
 - CFB Frequency = post-treatment measurement – baseline
 - Max Severity= define the maximum severity for each subject (none, mild, moderate, or severe) over the period since the previous visit.
 - Inhaler or rescue med (number of reports) count= count the number of reports where resp_rxn_inhaler >0 OR resp_rxn_add_tx_yn=Yes
 - CFB Inhaler or rescue= post-treatment measurement – baseline

- Frequency and Severity of Chronic Sinusitis (Sinus Infection Questionnaire)
 - Antibiotic use Frequency (number of reports) count= count the number of reports over the period since the previous visit where sinus_inf_antibio=yes
 - CFB Antibiotic use= post-treatment measurement – baseline

Pharmacodynamic Variables and biomarkers

- Plasma - Data from third party vendor
 - ScD10L (pg/mL)
 - Sp_selection (ng/mL)
- Biomarkers - Data from third party vendor.
 - Urine LTE4 (ng/mg Creatinine)
 - Urine PGD-M (ng/mg Creatinine)
 - Urine TX-M (ng/mg Creatinine)
 - Plasma F2 Isoprostanes (ng/mL)
 - Serum LTB4 (ng/mL)
 - SAM-Eicosanoids PGD2 (ng/mL)
 - SAM-Eicosanoids PXA2 (ng/mL)
 - SAM-Eicosanoids F2 Isoprostanes (ng/mL)

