- Dispense subject diary, provide instructions for daily use and remind subject to bring it to the next visit.
- Schedule appointment for next visit

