#### If the subject meets all inclusion and does not meet any exclusion criteria:

- Subject will be randomized
- PNIFR and FeNO will be recorded
- Perform serum/urine pregnancy test (for women of childbearing potential). Confirm subject is protected by one of the following acceptable forms of effective contraception during the study:
  - Established use of oral, injected or implanted hormonal contraceptive
  - "Double barrier" methods (i.e., Double Intrauterine device with copper or intrauterine system with progestogen and barrier contraceptive [condom, diaphragm or cervical/vault caps] used with spermicide [foam, gel, film, cream or suppository])
  - Female sterilization (e.g., tubal occlusion, hysterectomy or bilateral salpingectomy)
  - Male sterilization with post-vasectomy documentation of the absence of sperm in the ejaculate; for female subjects enrolled in the study, the vasectomized male partner should be the sole partner for that subject
- Perform blood sampling (prior to administration of IMP) for clinical laboratories: hematology, chemistry, PT, and INR.

Note: Clinical laboratory testing at Week 0 Visit is limited to biomarkers in serum and plasma if screening labs were performed within three weeks of starting IMP treatment.

- Collect urine and blood samples for eicosanoid metabolites.
- Collect nasoabsorptive matrix for eicosanoid measurements.

- Conduct a smell test (UPSIT)
- Collect data from subject diary and remind subject to record daily medication usage including IMP, exacerbations, rescue medication or antibiotic usage, if applicable, twice daily TNSS (AM and PM) and to bring their diary to the next visit
- Pre-IMP Dietary Assessment
- Dispense IMP and administer IMP
- Commence AE reporting
- Schedule appointment for next visit

Treatment Period (Week 0 to Week 8): Subjects will take ifetroban or placebo daily for eight weeks. There will be a telephone encounter one week into this Treatment Period to ensure safety and confirm that baseline asthma symptoms have not worsened.

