#### 8.1.3 Post-treatment Period

After two weeks post-treatment, subjects will return to the site for Week 10 Post-treatment Visit.

- Record all medication use with start date and dose and check for prohibited medications.
- Inquire about AEs/SAEs
- Perform a limited physical exam with vital signs (blood pressure, heart rate, respiration rate, body temperature, weight)
- Administer TNSS, ACQ-7, and SNOT-22
- Obtain spirometry, PNIFR and FeNO
- Perform blood sampling for clinical laboratories if abnormal at Week 8 only: hematology, chemistry, PT, and INR.

- Collect urine and blood samples for eicosanoid metabolites.
- Collect nasoabsorptive matrix for eicosanoid measurements.
- Conduct a smell test (UPSIT)
- Review subject diary for content and completeness; collect data from subject diary
- Propose the optional qualitative self-assessment of the treatment to the subject

Table 8–1 Schedule of Treatment & Events

	Screening Period	Treatment Period			Post-treatment Period	
	Visit(s)	Visit	Phone Call	Visit	Visit	Visit
	Week -3 to Week 0	Week 0	Week 1	Week 4 (± 5 days)	Week 8 (± 5 days)	Week 10 (± 5 days)
Informed Consent	X					
Inclusion/Exclusion Criteria	X					
Medical & Surgical History	X					
Subject Demography	X					
Physical Exam with vital signs	X					
Limited Physical Exam with vital signs		X		X	X	X
Spirometry (FEV1)	X	X		X	X	X
PNIFR and FeNO		X		X	X	X
Pregnancy Test (Serum/Urine) a	X	X		X	X	X
Hematology b	X	X d			X	Xe
PT, INR, Chemistry c	X	X d			X	Xe
SNOT-22, TNSS, ACQ-7	$X^{\mathrm{f}}$	X		X	X	X
Smell test (UPSIT)		X		X	X	X
Collect urine & blood for eicosanoid levels		X		X	X	X
Collect nasoabsorptive matrix for eicosanoid levels		X		X	X	X
Self-assessment of the treatment (optional)					X	
Dispense IMP		X		X		
IMP Dosing	II Ontinual Once Daily Dosing (200 mg/day)I					
Record Concomitant Medications	II					
AE/SAE Recording (if any)		II				
Dispense, review and/or collect subject diary		X		X	X	X

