# 16.6 Total Nasal Symptom Score (TNSS)

Please answer all the questions to the best of your ability twice daily, once in the morning after waking up and a second time before bedtime.

$0 = NONE \qquad 1 = M$	ILD 2	2 = MO	DERA	ΓE 3	= SEVE	CRE		
	Date:		Date:		Date:		Date:	
	AM	PM	AM	PM	AM	PM	AM	PM
Please rate how your nasal congestion								
has been over the past 12 hours:								
Please rate how your runny nose has								
been over the past 12 hours:								
Please rate how your nasal itching								
has been over the past 12 hours								
Please rate how your sneezing has								
been over the past 12 hours:								
Please rate how difficult has it been								
with nasal symptoms to sleep or go								
about your day's activities:								

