6.3 Dosing and Extent of Exposure

Exposure and compliance will be summarized for the Safety Population by treatment group and overall. Comments recorded on the Compliance CRF page regarding dosing will not be applied in the computation of compliance. Exposure is the duration (days) of treatment, computed as:

Exposure= Date of Final Dose- Date of Baseline Visit + 1.

Treatment compliance will be calculated as:

Compliance (%) = 100*(Total Number of Capsules Dispensed-Total Number of Capsules Returned)/Exposure.

Summary statistics for exposure and compliance will be presented in a table with the corresponding listing for the Safety Population.

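### SAP 4.6 sets no pre-dose cut-off for the PM baseline TNSS, and both schedule tables disagree with protocol 8.1.1 on when the diary starts

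*SAP*

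**What the plan says.** **The baseline window.** SAP 4.6 builds AM and PM visit scores separately and sets the baseline as follows: "Baseline Visit Score for AM and PM is obtained by averaging over the screening period and the day of the baseline visit". It names no cut-off relative to the first dose. The next window opens a day later: "Week 4 Visit Score is obtained by averaging over the day after the baseline visit to the day of the Week 4 visit".

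**The first dose.** At the Week 0 visit, once eligibility is confirmed and the subject is randomized, protocol 8.1.2 instructs the site: "Dispense IMP and administer IMP". SAP 6.3 is consistent with this and counts exposure from the same date: "Exposure= Date of Final Dose- Date of Baseline Visit + 1".

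**The ratings.** Protocol 16.6 asks for TNSS "twice daily, once in the morning after waking up and a second time before bedtime". The symptom items ask how the symptom "has been over the past 12 hours".

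**The diary.** The screening text in protocol 8.1.1 says: "Dispense subject diary, provide instructions for daily use and remind subject to bring it to the next visit". In Table 8-1 the row "Dispense, review and/or collect subject diary" has its first tick at Week 0 and none under Screening. The schedule in SAP 4.4 shows the same.

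**Use of the baseline.** Baseline TNSS is subtracted to give the change (SAP 4.6) and is the only covariate in the TNSS ANCOVA (protocol 11.6.3.2, SAP 7.2). It is also a covariate in the exploratory subgroup models for SNOT-22 (SAP 7.3).

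**The concern.** A baseline used for change scores and as an ANCOVA covariate should be measured before treatment. The evening rating on the Week 0 day is made after the first dose. Because the Week 4 window starts the next day, that rating counts only as baseline. If the drug has already begun to work that evening, part of its effect is subtracted from itself and the covariate is no longer independent of treatment.

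The schedule tables add a second problem. A site working from the table rather than from 8.1.1 would not issue the diary until Week 0 and would have no pre-dose diary TNSS. Under the SAP definition its PM baseline would then rest on the Week 0 evening alone, and it would have no AM diary baseline. The rule in SAP 5.1 for a missing baseline, which falls back on screening, would not help: footnote f of the schedule limits the screening questionnaires to SNOT-22. No planned table would reveal this either, because SAP 7.2 summarises TNSS at Weeks 4, 8 and 10 but not at Week 0.

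**Working it through.** **The plan's own figure.** The plan gives no sample-size or power figure for TNSS. The only one is for SNOT-22: SD 16, difference 12, two-sided 0.05, 90% power, 38 per group. It reproduces: 2 × (1.960 + 1.282)² × 16² / 12² = 37.4, rounded up to 38. Power at 38 per group is 90.5% by the normal formula and 89.7% by the noncentral t. Nothing below depends on it.

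**Order of events on the Week 0 day.** AM rating after waking, then the clinic visit and first dose, then the PM rating before bedtime. The AM entry is therefore pre-dose and the PM entry post-dose.

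**Share of the PM baseline that is post-dose.** Let s be the number of screening evenings with a diary entry. The share is w = 1/(s + 1). Screening lasts up to three weeks in protocol 7.1 (s = 21) and up to two weeks in SAP 4.1 (s = 14). Both are upper limits. The rows for 7, 3 and 1 evenings are assumptions about short diaries, and the row for 0 is a diary first issued at Week 0.

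**Effect on the treatment difference.** Let D be the true follow-up difference, f the first-evening effect as a fraction of D, and β the slope of follow-up on baseline.
- The expected baseline difference is w × f × D.
- A simple change-from-baseline difference becomes D × (1 − w × f), a loss of w × f.
- The ANCOVA difference becomes D × (1 − β × w × f), a loss of β × w × f.

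The documents give neither f nor β. I assume f from 0.25 to 1 and β from 0.3 to 0.7.

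| Screening evenings s | Share w | Loss, simple change, f = 0.25 | Loss, simple change, f = 1 | Loss, ANCOVA, f = 1, β 0.3–0.7 |
|---|---|---|---|---|
| 21 | 1/22 = 4.5% | 1.1% | 4.5% | 1.4–3.2% |
| 14 | 1/15 = 6.7% | 1.7% | 6.7% | 2.0–4.7% |
| 7 | 1/8 = 12.5% | 3.1% | 12.5% | 3.8–8.8% |
| 3 | 1/4 = 25% | 6.25% | 25% | 7.5–17.5% |
| 1 | 1/2 = 50% | 12.5% | 50% | 15–35% |
| 0 | 1/1 = 100% | 25% | 100% | 30–70% |

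For the AM score the post-dose share is 0 in every row where an AM baseline exists. If f = 0 the loss is 0 throughout.

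**The case against.** A reader might infer that the TNSS baseline is wholly post-treatment. The documents do not support that.
- Protocol 8.1.1 issues the diary at screening for daily use.
- The Week 0 text in 8.1.2 has the site collect diary data, which presupposes earlier entries.
- The SAP window itself averages over screening.

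Against these, the blank Screening cell looks like a clerical slip in a row that combines several actions. What remains is an ambiguity: the visit text first names twice-daily TNSS at Week 0, so the tables and the text still need to agree.

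Nor is the post-dose evening the only TNSS value available at Week 0. Protocol 8.1.2 lists a clinic TNSS before eligibility is reconfirmed, and so before randomization and dosing. The gap is that SAP 4.6 gives that value no role.

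A reader might also infer that the baseline counts of exacerbations, rescue use and antibiotic use fail if the diary starts late. That is not established. SAP 4.6 takes these from a respiratory reaction questionnaire and a sinus infection questionnaire, and the documents do not say that the diary is their only source. Interval history and medication use are also recorded at Week 0.

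Finally, a share of entries is not a bias. Attenuation needs a drug effect by the first evening, for which the documents give no figure, and the 12-hour recall means that even this entry may cover some pre-dose hours. Both points stand, and they make the concern smaller. They do not supply the missing cut-off.

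**Conclusion.** The point holds as one of definition and consistency, and it is minor. As written, SAP 4.6 counts one post-dose evening entry in the PM baseline TNSS and nowhere else. With a diary kept through screening, that entry is 4.5% (21 evenings) to 6.7% (14 evenings) of the PM baseline.

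If the full treatment effect were present by the first evening, the loss would be 4.5–6.7% of a simple change-from-baseline difference, or 1.4–4.7% under ANCOVA with slopes of 0.3 to 0.7. Those are upper values on the assumption that the first-evening effect is no larger than the later one. With a slower onset the loss is smaller, and with no drug effect there is no bias. The direction is always toward a smaller treatment difference.

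The conflict over when the diary starts is separate and real. The larger losses in the table apply only to subjects with few or no screening entries, and nothing in the documents shows that such subjects were intended.

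**What to change.** 1. In SAP 4.6, limit baseline TNSS to entries before the first dose: PM through the day before Week 0, AM through the Week 0 day. The calendar date is enough, so no dosing time is needed. State whether the Week 0 evening entry is dropped or opens the Week 4 PM window.
2. Reconcile the diary row in Table 8-1 and SAP 4.4 with protocol 8.1.1, and say in 8.1.1 whether twice-daily TNSS starts at screening.
3. State the fallback for a subject with no screening diary entries, for example the clinic TNSS given before randomization at Week 0. Without one, the new cut-off leaves such a subject with no PM baseline. The rule must say how one clinic value stands in for the separate AM and PM averages.
4. Add Week 0 to the TNSS summaries in SAP 7.2, with the number of entries per subject, so that thin or missing baselines can be seen.

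The cost is SAP wording, one cell in each of two tables and one extra summary time point. No new procedure or data collection is needed. SAP section 1 already allows revision before any unblinded analysis.

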# 7 STUDY DESCRIPTION

# 7.1 Study Design

[figure not shown]
CPI-IFE-006 is a randomized, double-blind, placebo-controlled Phase 2 study to evaluate oral ifetroban administered daily for eight weeks in symptomatic AERD subjects.

Approximately 76 subjects will be randomized into two treatment groups of 38 subjects per group.

The clinical study will be conducted with 3 periods:

- Screening period of up to three weeks
- Randomized ifetroban/placebo treatment period of eight weeks
- Post-treatment period for safety and efficacy of two weeks

Figure 7-1 Study Design

ACQ = Asthma Control Questionnaire; FeNO = Fractional exhaled nitric oxide; FEV1 = forced expiratory volume in one second; PBO = placebo; PD = pharmacodynamic; PNIFR = peak Nasal Inspiratory Flow Rate; SNOT = Sinonasal Outcome Test; TNSS = Total Nasal Symptom Score; UPSIT = Smell Identification Test

The total duration of the study participation for each subject is up to 13 weeks. Recruitment is planned to stop when approximately 76 subjects are randomized. The end of the study is defined as the last subject's last visit/contact.

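### Exacerbation, rescue and antibiotic reports are raw counts over unequal windows, so if baseline is the screening period the within-arm change summaries can show worsening at Weeks 4 and 8 when the rate is constant

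*SAP*

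**What the plan says.** SAP 4.6 gives three definitions based on report counts.

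- Asthma exacerbations: "Subject Frequency =count the number of reports since the previous visit for each visit", with "CFB Frequency = post-treatment measurement – baseline".
- Rescue use: "Inhaler or rescue med (number of reports) count= count the number of reports where resp_rxn_inhaler >0 OR resp_rxn_add_tx_yn=Yes". No period is stated.
- Antibiotic use: "count the number of reports over the period since the previous visit where sinus_inf_antibio=yes".

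Neither document gives a denominator, rate or offset for these variables. The SAP 7.2 table summarises the counts and their changes at Weeks 0, 4, 8 and 10, with LOCF listed for each row. It plans ANCOVA on the change in exacerbation, rescue and sinusitis reports. As the table reads, the ANCOVA for antibiotics is on the raw count, and the change is summarised only. The sinusitis report count appears in 7.2 without a definition of its own in 4.6.

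The same section treats TNSS differently: "The daily score for AM and PM are averaged over time between the visits separately". For TNSS it also fixes the baseline window: "Baseline Visit Score for AM and PM is obtained by averaging over the screening period and the day of the baseline visit". No baseline window is given for the counts.

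SAP 4.1 has "Screening period of up to two weeks"; Protocol 7.1 has "Screening period of up to three weeks". Protocol 8.1.2 and 8.1.3 place the later visits so that the intervals are nominally 4, 4 and 2 weeks.

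**The concern.** A raw count grows with the time over which it is collected. Subtracting a count over two or three weeks from a count over four weeks mixes any real change in rate with the difference in window length. Whether ifetroban reduces exacerbations, rescue use and antibiotic use is a secondary objective (SAP 3.2). A reader of the planned change tables could see both arms apparently worsening on treatment, or a real reduction in one arm shown as no change.

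LOCF adds a second mismatch. A count from a 4-week interval can be carried into the 2-week interval that ends at Week 10.

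**Working it through.** The documents give no event rate and no stated result for these variables, so there is no figure of the plan's own to reproduce. The weekly rate r is an assumption, shown over a range. The sign at Weeks 4 and 8 does not depend on it.

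**Inputs.** Baseline window b: up to 2 weeks (SAP 4.1, 4.4) or up to 3 weeks (Protocol 7.1, 8.1). Follow-up window w: 4 weeks at Week 4, 4 at Week 8 and 2 at Week 10. Assumption: the baseline count covers screening.

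**Constant rate.** Expected change = r × (w − b).

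| Baseline | Weeks 4 and 8 | Week 10 |
|---|---|---|
| 1 week | (4 − 1)r = +3r | (2 − 1)r = +r |
| 2 weeks | (4 − 2)r = +2r | (2 − 2)r = 0 |
| 3 weeks | (4 − 3)r = +r | (2 − 3)r = −r |

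For r = 0.1, 0.25 and 0.5, the Week 4 or 8 change is +0.20, +0.50 and +1.00 (2-week baseline), or +0.10, +0.25 and +0.50 (3-week).

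**Rate truly halved.** Expected change at Weeks 4 and 8 = 4 × r/2 − b × r. With b = 2 this is 0. With b = 3 it is −r, so the count falls from 3r to 2r: 33%, not 50%. With b = 1 it is +r.

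**Break-even.** The mean change is negative only if the new rate x satisfies 4x < b × r. The rate must therefore fall by more than 50% (b = 2), 25% (b = 3) or 75% (b = 1).

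**Individual subjects.** With independent Poisson counts at constant r = 0.25, 47% rise and 18% fall at Week 4 or 8 (2-week baseline), or 40% and 27% (3-week). If subjects' rates vary (gamma, shape 2), the shares are 42% and 16%, or 36% and 23%.

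**LOCF into Week 10.** At a constant rate the carried count has mean 4r where an observed one has mean 2r, so it is doubled.

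**Visit windows.** With ±5 days (protocol) the Week 4 to Week 8 interval can run from 28 − 10 = 18 to 28 + 10 = 38 days. With ±2 days (SAP 4.4) it runs from 24 to 32.

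**Between arms.** Simulation: 38 per arm, gamma-Poisson counts with mean 0.25 per week, equal follow-up, ANCOVA on the change in count with baseline count and treatment, 5,000 runs.

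- No treatment effect: mean change about +0.50 in both arms (2-week baseline) or +0.25 (3-week). The test rejected in 4.9% and 4.2% of runs.
- Rate halved on ifetroban, 2-week baseline: mean change about 0.00 on ifetroban and +0.50 on placebo, difference −0.49.
- Per week observed, the changes in that halved-rate case were about −0.13 on ifetroban and 0.00 on placebo.

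**The case against.** The strongest reply is that inference hardly suffers. The windows are the same in both arms, the ANCOVA contrast keeps its error rate, and a halved rate still gives a clear between-arm difference. The distortion appears equally in the placebo column, and the visit schedule is there to be read. This stands, and it limits the point to how within-arm and cross-visit summaries read.

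A reader might infer that the treatment comparison itself is biased. The documents do not support that. It would need shortened or carried counts to occur unequally by arm. The documents give no dropout rates and do not say under which week an early-termination count is filed. In simulations with assumed dropout, shortened counts filed under Week 8 and r from 0.1 to 1.0, 15% against 10% gave differences of at most about 0.1 reports and type I error near 5%. Only at 30% against 10% did it reach about 8%.

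A reader might also infer that the tables will certainly show worsening. That is too firm. SAP 4.6 sets no baseline window for the counts, and the questionnaires it names are not reproduced. The diary start also conflicts: Protocol 8.1.1 dispenses the diary at screening and 8.1.2 collects its data at Week 0, but Protocol Table 8-1 and SAP 4.4 first mark it at Week 0. With another baseline, the size and even the sign could change.

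Lastly, entry criteria exclude recent severe asthma events (Protocol 7.4.1, 8.1.1; SAP 4.2). Baseline counts may be low by selection, so some rise could remain after dividing by days. This also stands. Part of the difference in screening length may reflect document versions, since SAP 1 names the protocol dated 24 January 2017; the windows are unequal under either length.

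**Conclusion.** The point holds as a minor defect in secondary or ancillary summaries. If the baseline count covers screening, the within-arm changes at Weeks 4 and 8 are shifted upward by r to 2r with full-length screening, and by 3r with one week. At Week 10 the shift is 0 or −r with full 2- or 3-week screening. The shift follows from window length alone, given a constant rate; only its size depends on the assumed r. The randomised contrast is not biased when follow-up is similar by arm, and the primary SNOT-22 analysis is not touched. Confidence is medium, because the baseline window has to be inferred.

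**What to change.** In SAP 4.6 and 7.2:

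1. Report exacerbation, rescue, sinusitis and antibiotic counts per 28 days observed, with arm summary = total reports ÷ total days, and express change on that scale.
2. Do not apply LOCF to these counts. For subjects who stop early, use the days actually observed.
3. Define the baseline window as for TNSS and give the rescue count the same interval as the others. First reconcile the 2- and 3-week screening statements and the diary start.
4. Replace the subject-level ANCOVA on these counts and their changes with a quasi-Poisson or negative binomial model, with log days observed as offset and baseline rate as covariate.
5. State the interval length beside the Max Severity summaries for asthma and sinusitis, which cover the same unequal windows.

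Add a note that the entry criteria may leave some rise from baseline even after normalising, so the between-arm comparison should carry the conclusion.

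The cost is SAP wording and extra code; visit dates are already collected. SAP 1 allows revision before any unblinded analysis. Whether screening-period reports exist depends on item 3. Individual rates from very short follow-up are unstable, which is why arm totals are preferred. The gain is a correct scale rather than a better-calibrated test: in the dropout simulations a quasi-Poisson test with offset had type I error of 4.6% to 6.2%.
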